4.2 Rationale for study design, doses and control groups

The study will be carried out in subjects with T2DM to allow for results applicable in the target population ie, subjects with T2DM failing on the first line of treatment, Metformin. Before proceeding into larger studies, the availability and security of effective treatment for severe hypoglycaemia are important to define. The CR response, safety aspects and recovery after hypoglycaemia are being assessed in healthy volunteers with unaffected insulin secretion (ie, highly responsive to GK stimulation). The current study will provide important complementary information on these aspects in T2DM patients as well as a comparison between spontaneous recovery from hypoglycaemia with recovery induced by administration of the pancreatic hormone glucagon.

Each subject with T2DM will receive AZD1656 at maximal tolerated dose on top of their normal dose of Metformin. In both hypoglycaemic clamp periods, giving the total daily dose of AZD 1656 and the normal morning dose of Metformin, will induce hypoglycaemia after an overnight fast. For safety reasons as well as to guarantee comparable degrees of hypoglycaemia in both study groups, a hypoglycaemic clamp method will be applied where glucose and insulin will be infused as required in response to a continuous plasma glucose measurement by an automated device, the Biostator[®]. Thereby, plasma glucose levels will be decreased in a step-wise controlled fashion and severe hypoglycaemia with plasma glucose 2.7 mmol/L will not be allowed.

The study subjects will be randomised to receive either an intramuscular dose of glucagon or to participate in a control arm where the recovery from hypoglycaemia is dependent on the CR response. Subjects will then crossover to the reverse treatment in the second hypoglycaemic period after a two days recovery period when the same dose of AZD1656 will be given as during Day 3 and 4 to ensure similar physiological conditions both treatment periods.

A follow-up visit will be conducted within 7 to 10 days after the last dose to assure that all study subjects have a stable glycaemic control and are otherwise healthy leaving the study.

This study is open, thus no blinding of treatment will be done. The primary variable will be assessed by investigation of laboratory variables and the secondary variables will be measurements of time to recovery from hypoglycaemia, which results are independent of blinding. Furthermore, in this crossover design the T2DM study subjects are their own controls.

The daily AZD1656 dose, 80 mg or 160 mg, is within the dose span studied in the early clinical development program for AZD1656.

To challenge the CR response, it is of utmost importance that the selected dose AZD1656 results in a plasma glucose nadir of 2.7 mmol/L, a glucose level that induces a CR response in hormones (D0280C00003). In order to increase the likelihood of reaching this nadir, all study subjects will start at a AZD1656 dose of 40 mg bid and will be titrated to 80 mg bid if tolerated as defined in the protocol. If administration of the highest tolerated total daily dose of AZD1656 as a single dose is insufficient for inducing the intended reduction of plasma glucose, insulin infusion will be used as needed. As a safety measurement, a glucose infusion will be continuously titrated to avoid prolonged and severe hypoglycaemia.

5. SUBJECT SELECTION CRITERIA

Subject population should be selected without bias.

Investigator(s) must keep a record of subjects who entered pre-trial screening but were never enrolled eg, subject screening log. Each subject must meet all of the inclusion criteria and none of the exclusion criteria for this study. Under no circumstances can there be exceptions to this rule.

5.1 Inclusion criteria

For inclusion in the study subjects must fulfil the following criteria.

1. Provision of informed consent prior to any study specific procedures
2. Men or women of non-childbearing potential (postmenopausal, and/or have undergone hysterectomy and/or bilateral oophorectomy or salpingectomy/ tubal ligation) aged ≥ 18 to ≤ 75 years. Women will be defined as postmenopausal if last menstruation period was >1 year ago and serum follicle stimulating hormone (FSH)

is within the postmenopausal range, or if age >50 years and with last menstruation period >2 years ago

3. Body mass index between ≥ 19 and ≤ 40 kg/m²
4. T2DM diagnosis confirmed by C-peptide >0.3 nmol/L and no glutamic acid decarboxylate (GAD) antibodies at enrolment (screening)
5. Treatment with Metformin alone with a total daily dose not less than 1000 mg. Stable glycaemic control indicated by unchanged treatment within 3 months prior to enrolment
6. HbA1c $\leq 9,5\%$ at enrolment (HbA1c value according to international Diabetes Control and Complications Trial [DCCT] standard)
7. Subjects should have a fasting plasma glucose (FPG) in the range of 6,0 to 11,0 mmol/L) at screening

5.2 Exclusion criteria

Subjects must not enter the study if any of the following exclusion criteria are fulfilled:

1. Participation in another clinical study during the last 30 days prior to enrolment
2. History of ischemic heart disease, symptomatic heart failure, stroke, transitory ischemic attack or symptomatic peripheral vascular disease
3. Positive test for Hepatitis B surface antigen or antibodies to human immunodeficiency virus (HIV) or antibodies to Hepatitis C virus
4. AST or alanine aminotransferase (ALT) laboratory results >3xULN
5. History of psychiatric or somatic disease/condition (eg, gastrointestinal disease) that may interfere with the objectives of the study, as judged by the investigator
6. Signs of diabetic proliferative retinopathy or diabetic maculopathy, at screening or on an ophthalmological examination within 3 months from start of study
7. History or ongoing symptoms/signs of severe allergy/hypersensitivity as judged by the investigator
8. History of malignancy within the last 5 years, excluding successful treatment of basal or squamous cell skin carcinoma or in-situ carcinoma of the cervix
9. Impaired renal function in terms of Glomerular Filtration Rate <60 ml/min, based on Modification of diet in renal disease (MDRD) study calculation ([Levey et al 2003](#))

10. Past or present alcohol or drug abuse within the last 5 years or excessive intake of alcohol of greater than 15 units/week or positive test in drugs of abuse screens
11. Systolic blood pressure (BP) >160 mmHg or diastolic BP >95 mmHg at screening
12. Any ongoing oral anti-diabetic treatment apart from Metformin within 8 weeks prior to randomisation
13. Changes in any current medication (initiation, dose change or cessation), within the last 4 weeks prior to randomisation. The criterion does not apply to medication prescribed for occasional use
14. Use of insulin, glitazones, warfarin, amiodarone within 3 months prior to enrolment (screening) and use of potent Cytochrome 450 (CYP450) inhibitors, eg, ketoconazole and macrolide antibiotics within 14 days before randomisation
15. Use of anabolic steroids and systemic treatment with glucosteroids within 3 months before enrolment (inhaled and local treatment allowed)
16. Blood loss in excess of 450 mL 3 months prior to enrolment
17. Intake of another investigational drug within 30 days (or at least five t_{1/2} of the drug) before the first administration of the IPs
18. Previous randomisation to treatment in the present study
19. Previous intake of the IP tested in this study, AZD1656
20. Current smokers who smoke more than 10 cigarettes per day (or equivalent use of tobacco products) or cannot give up smoking for duration of in-patient period
21. Involvement in the planning and/or conduct of the study (applies to both AZ staff and/or staff at the study site)
22. Subject has a sibling participating in the same study
23. Clinically significant neuropathy according to the investigator
24. Suspected or confirmed poor protocol or medication compliance as judged by the investigator
25. Any clinically significant abnormality identified on physical examination, laboratory tests or electrocardiogram (ECG), which in the judgment of the investigator would compromise the patients' safety or successful participation in the clinical study

The following is regarded as criteria for exclusion from the genetic component of the study:

1. Previous bone marrow transplant
2. Whole blood transfusion within 120 days of the date of genetic sample collection

5.3 Procedures for handling incorrectly included subjects

Subjects that do not meet the inclusion/exclusion criteria for a study should not, under any circumstances, be enrolled into the study– there can be no exceptions to this rule.

Where subjects that do not meet the study criteria are enrolled in error, incorrectly randomised, or where subjects subsequently fail to meet the criteria for the study post enrolment, the procedures included in the protocol for the discontinuation of such subjects must be followed. These procedures must be included in the protocol and must take into consideration ethical and safety factors and how these subjects will be treated in the analyses.

Once the error is identified a discussion must occur between the AZ SDT Physician and the Investigator regarding whether to continue or discontinue the subject from the study. The AZ SDT Physician is to ensure all such decisions are appropriately documented. In situations where an agreement cannot be reached, the subject should have their randomised therapy stopped and be discontinued from the study.

5.4 Withdrawal of subjects

5.4.1 Criteria for discontinuation from the study

Subjects may be discontinued from study treatment and assessments at any time. Specific reasons for discontinuing a subject are:

- Voluntary discontinuation by the subject who is at any time free to discontinue his/her participation in the study, without prejudice to further treatment
- Risk to subjects as judged by the investigator and /or AZ
- Severe non-compliance to protocol as judged by the investigator and/or AZ
- Incorrectly enrolled subjects
- Subject lost to follow-up
- Adverse Events
- Withdrawal of informed consent to the use of biological samples collected as an integral part (including the optional genetic sample) of the study, see Section 8.5

5.4.2 Procedures for discontinuation of a subject from the study

A subject that discontinues will always be asked about the reason(s) for discontinuation and the presence of any AE. If possible, they will be seen and assessed by an investigator(s). AEs will be followed up (See Sections 7.3.3 and 7.3.4).

5.4.3 Study specific criteria for discontinuation

Events of hypoglycaemia (defined as plasma glucose <2.5 mmol/L (45 mg/dL), at 2 occasions or 1 event of hypoglycaemia that is difficult to cure despite glucose administration (according to the judgement of the investigator) or prolonged hyperglycaemia (defined as 2 consecutive days with fasting morning plasma glucose >15 mmol/L (270 mg/dL) should lead to discontinuation of treatment and the event should be reported as AE.

6. STUDY CONDUCT

6.1 Restrictions during the study

Subjects will have to comply with the following restrictions:

1. Day 5 and 8: Fast (except for water) from 2200 (10 pm). Subject will be allowed to drink a moderate amount (<500 mL) of water from midnight until morning dose of IPs
2. Abstain from tobacco/nicotine-containing substances and refrain from alcohol within 12 hours prior to and during the clinic visit
3. Abstain from blood and plasma donation during the study and up to 3 months after completion of the study
4. The subjects should neither start any new physical training nor increase the intensity of their usual physical training during the study (from pre entry to follow up)
5. Male subjects should use appropriate contraceptive (double barrier method or vasectomy) from the 1st administration of the IP and refrain from sperm donation until at least 3 months after the last dose, since no data on male reproduction is available
6. Subjects should eat standard, BMI corrected, weight maintained diet during the residential period, except from day 5 and 8

6.2 Subject enrolment and randomization

The PI will:

1. Obtain signed informed consent from the potential subject before any study specific procedures are performed

2. Assign potential subject a unique enrolment number, beginning with “E0001001”
3. Determine subject eligibility. See Sections 5.1 and 5.2
4. Assign eligible subject unique randomization code (subject number), beginning with “101”

Randomisation codes will be assigned strictly sequentially as subjects are eligible for randomisation.

If a subject discontinues participation in the study, then his/her enrolment/randomisation code cannot be reused.

If subjects have discontinued their participation in the study then they cannot re-enter into the study.

6.2.1 Procedures for randomization

A randomisation scheme will be computer generated by AZ R&D Mölndal using the global randomisation system (GRand).

The subjects will be randomised to the two treatment sequences AB and BA in equal proportion. (A = 1 mg Glucagon i.m; B = control, ie, spontaneous CR response). The randomisation will be performed in blocks.

A total of 10 subjects will be randomised to the two treatment arms.

6.3 Blinding and procedures for unblinding the study (Not Applicable)

6.4 Treatments

6.4.1 Identity of investigational product(s)

| Investigational product | Dosage form and strength | Manufacturer | Formulation number |
|-------------------------|-----------------------------|-----------------|--------------------|
| AZD1656 | Oral Suspension 25 mg/mL | AstraZeneca R&D | H 2001-01-01 |

Oral suspension of AZD1656 will be prepared by AstraZeneca R&D, Sweden. Before dosing the AZD1656 suspension will be diluted if needed to obtain the correct dose volume according to the handling instructions. Purified water will be used as dilution media. AZD1656 25mg/mL oral suspensions will be supplied in vials of 20 mL containing 10 mL oral suspension as bulk supply. One vial of AZD1656 oral suspension can be used to more than one (1) subject. Further information will be available in the handling instructions that will accompany the IP.

6.4.2 Doses and treatment regimens

The Metformin treatment will be provided by the site 8 days before subjects start the treatment with AZD1656 (Visit 3). All subjects will be given the same generic commercial Metformin immediate release formulation (major brand). Commercial Metformin in original packages will be purchased locally by the Clinical Research Organisation (CRO) and will be labelled by the study site personnel.

The Metformin will be administered once or twice daily with the first dose in the morning. If the subject normally takes Metformin more than twice daily, half the total daily dose will be administered bid, with the first dose in the morning and the second dose in the evening. If the subject normally takes Metformin once daily the total daily dose will be administered in the morning.

The Metformin dose should be taken after IP in the morning (before breakfast) and, if applicable, before dinner (9 hours later), after the second daily dose of IP.

At Visit 3, Day 1, all subjects will start their AZD1656 treatment with a titration period where they will receive oral solution of AZD1656 40 mg bid for one day on top of their Metformin treatment. Day 2 they will receive 80 mg bid, and, if tolerated, continue with that dose for another 2 days or, if not tolerated, maintain the dose of 40 mg bid for another 2 days. On Day 5 each subject will be randomised to the two treatment regimens AB or BA in random order. On Day 5 and Day 8 the AZD1656 dose, the total daily dose of 80 mg or 160 mg, will be given as a single dose in the morning after an overnight fast.

The suspension will be administered with the subjects in an upright position and the container will be rinsed with 2x30 mL of tap water to collect the remainings of the study drug in the container. The subjects will then drink an extra glass (150 mL) of tap water.

The A treatment includes an intra muscular injection of 1 mg glucagon at 3 hours post dose. Glucagon will be purchased locally in commercially available packages by the CRO, and will be labelled by the study personnel.

During Day 6-7 the subjects will receive the same dose of AZD1656 oral solution bid as on Day 3 and 4.

Insulin solution for intravenous use during the Hypoglycemic Clamp will be locally purchased by the CRO, Profil.

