- To assess the CR response (norepinephrine, epinephrine, glucagon, cortisol and growth hormone) during hypoglycemia in T2DM patients treated with Metformin
- To collect and store deoxyribonucleic acid (DNA) for future exploratory research into genes that may influence drug response ie, distribution, safety, tolerability and efficacy of AZD1656 treatment

Study design

The total study period is approximately 4-8 weeks and includes four visits to the clinic.

[figure not shown]
A pre-entry visit (Visit 1) will take place within 28 days before randomisation. If the subjects are eligible to enter the study they will come to the clinic 8 days (Day –8, Visit 2) before Visit 3 to switch to the Metformin provided by the centre. The Metformin treatment will be maintained until the end of the residential period, Visit 3. A follow-up visit (Visit 4) will take place 7-10 days after Visit 3.

Each subject will start their Visit 3 by entering a titration phase of two days, starting at 40 mg twice daily (bid) for one day and increase to 80 mg bid, if tolerated, the second day. Thereafter the tolerated dose, 40 or 80 mg bid, will be maintained for two more days.

The subjects will then (Day 5) be randomised to one of two treatment arms in a cross-over manner, where the full daily oral dose of AZD1656 will be given in the morning under fasting condition to induce hypoglycaemia. The single dose will be followed by either a subsequent injection of glucagon or spontaneous recovery from hypoglycaemia by the CR response depending on treatment arm.

After a recovery phase of two days (Day 6 and 7) where AZD1656 will be maintained at the same dose bid as Day 3-4, subjects will be subjected to a new period of controlled hypoglycaemia, see [Figure S1](#).

Figure S1 Study design

A = Glucagon injection, 1 mg i.m.
B = Control, i.e. Spontaneous CR response

Plasma glucose, counter regulatory hormones and pharmacodynamic (PD) markers will be followed for 6 h post dose.

Target subject population

Men and non-fertile women with T2DM treated with Metformin will participate in the study. Ten subjects are planned to be randomised in order to get eight evaluable subjects.

Investigational product, dosage and mode of administration

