4.1 Overall study design and flow chart

In total, 10 T2DM patients treated with Metformin, aged ≥ 18 to ≤ 75 years, will participate in the study to ensure 8 evaluable patients, hereafter called subjects.

The total study period is approximately 4-8 weeks and includes four visits to the clinic, see [Figure 1](#).

Visit 3, treatment/residential period

Each subject will enter a titration phase of two days, with 7-point plasma glucose monitoring, starting at 40 mg bid for one day and increased to 80 mg bid, if tolerated, the second day. Thereafter the tolerated dose, 40 or 80 mg bid, will be maintained for two more days.

The subjects will then (Day 5) be randomised to one of two treatment arms in a cross-over manner, where the full daily oral dose of AZD1656 will be given in the morning under fasting condition to induce hypoglycaemia. The treatment sequence will be given in the randomisation list. The single dose will be followed by either a subsequent injection of glucagon or spontaneous recovery from hypoglycaemia by the CR response depending on treatment arm.

After a recovery phase of two days (Day 6 and 7) where AZD1656 will be maintained at the same dose bid as Day 3-4, subjects will be subjected to a new period of controlled hypoglycaemia followed by alternate treatment as to the previous hypoglycaemic study period, see [Figure 1](#).

On Day 5 and 8, after an overnight fast, the full daily dose from Day 3-4 (80 mg or 160 mg) will be given as a single oral dose (time 0 min). Blood samples for glucose and hormone analyses will be drawn from a catheter in a cubital vein. Another vein will be used for infusion of insulin and/or glucose, controlled by the Biostator[®], in order to reach glycaemic plateaus of 5 mmol/L (0 to 60 min), 4 mmol/L (60 to 90 min), and 3.2 mmol/L (90 to 150 min). Plasma glucose will then be clamped to a target nadir of 2.7 mmol/L and released at 180 min, ie, insulin infusion will be stopped, see [Figure 3](#).

The fasting state will be maintained 270 min after dosing. Plasma glucose will be followed continuously. When plasma glucose has been clamped aiming at 2.7 mmol/L for 30 minutes (ie, 180 min after dose), the clamp will be released and either 1 mg glucagon will be

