4.1.1 Titration procedure

The dose of AZD1656 will be individually titrated stepwise provided that the glucose values of the subject are within acceptable limits. The decision to increase the dose on study Day 2 (dose titration) and the decision to continue on the individual tolerated dose on study Day 3-4 will be based on the morning fasting glucose on the actual day and the post-prandial glucose values from the previous day ([Figure 2](#)). After Day 2 no further dose increases are allowed, but down-titration to 40 mg bid may be needed. Study specific discontinuation criteria applies for hypoglycaemia or pronounced hyperglycaemia as described in [Section 5.4.3](#).

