4.1.2 Rescue treatment – Low plasma glucose outside titration period

The following section applies during the residential period of the study (Visit 3), excluding 0-6 hours post dosing with AZD1656 on study Day 5 and 8.

If the subject experiences hypoglycaemic symptoms, a plasma glucose measurement should be obtained (before any treatment) and the subject should be treated according to local practice. For subjects with hypoglycaemia, defined as P Glucose <2.5 mmol/L (45 mg/dL), approximately 25 g glucose (juice) orally should be given as rescue treatment. Intravenous glucose could also be considered according to the judgement of the investigator.

If recurrent hypoglycaemia (defined as P-Glucose <2.5 mmol/L [45 mg/dL]), or hypoglycaemia that is difficult to cure, the subject should be discontinued from the study, Section 5.4.3.

If rescue treatment is needed during titration of investigational product (IP), the dose of AZD1656 should be reduced, see Figure 2. If rescue treatment is needed already after the initial dose the subject should be discontinued from the study.

Figure 1 Study design

[figure not shown]
[figure not shown]

Figure 2 Dose titration and glucose value

Note: the titration period is limited to Day 1 and Day 2 for each subject. On Day 3 the dose will be kept or reduced if needed.

Figure 3 Overview step wise hypoglycaemic clamp

[figure not shown]

Table 1 Study plan

| Event | Enrolment | Metfor- min treatment | Titration period | Maintenance period | Hypo- glycemic Clamp period 1 | Recovery period | Hypo- glycemic Clamp period 2 | Follow- up |
|--|--|-----------------------------|---------------------|-----------------------|--|--------------------|--|----------------------------------|
| Visit | 1 | 2 | 3 | 3 | 3 | 3 | 3 | 4 |
| Study Day | ≤28 days before rando- misation | Day -8 | D1-D2 | D3-D4 | D 5 | D 6-7 | D 8 | 7-10 days after Visit 3 |
| Informed consent | X | | | | | | | |
| Inclusion/exclusion criteria | X | | | | X | | | |
| Medical and surgical history including T2DM history | X | | | | | | | |
| Physical examination | X | | | | | | | X |
| Ophtamologic examination ^a | X | | | | | | | |
| Laboratory screening | X ^b | | X ^c | | X ^c | X ^c | X ^c | X |
| C-peptide, HbA1c & GAD antibodies | X | | | | | | | |

| Event | Enrolment | Metfor- min treatment | Titration period | Maintenance period | Hypo- glycemic Clamp period 1 | Recovery period | Hypo- glycemic Clamp period 2 | Follow- up |

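### Section 6.4.2 gives every subject 80 mg bid on Day 2, whereas Section 4.1.1 makes that increase a glucose-based decision and Sections 4.1 and 4.2 make it depend on tolerance

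*Protocol*

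**What the plan says.** Section 6.4.2 (Doses and treatment regimens) starts all subjects on 40 mg bid on Day 1. It then continues: "Day 2 they will receive 80 mg bid, and, if tolerated, continue with that dose for another 2 days". The alternative branch reads "if not tolerated, maintain the dose of 40 mg bid for another 2 days". This text does not refer to Section 4.1.1 or to Figure 2.

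Elsewhere the protocol attaches the condition to the increase itself:

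- Synopsis, Study design: "increase to 80 mg bid, if tolerated, the second day".
- Section 4.1: "starting at 40 mg bid for one day and increased to 80 mg bid, if tolerated, the second day".
- Section 4.2: all subjects start at 40 mg bid and "will be titrated to 80 mg bid if tolerated as defined in the protocol".
- Section 4.1.1 (Titration procedure): dose steps require glucose values within acceptable limits. The Day 2 increase and the choice of dose for Days 3 and 4 are named as two decisions. Both "will be based on the morning fasting glucose on the actual day and the post-prandial glucose values from the previous day". No increase is allowed after Day 2, but a step down to 40 mg bid is.

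**The concern.** Section 6.4.2 is where site staff would look for the dose to give. It keeps the second of the two decisions in Section 4.1.1 (which dose to carry into Days 3 and 4) and omits the first (whether to go up on Day 2). Someone dosing from Section 6.4.2 alone would give the higher dose on Day 2 to a subject whose glucose values called for no increase. Such subjects are the ones the titration rule is meant to protect, and the drug lowers glucose.

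There is also a reporting consequence. Section 1.2 treats any dose above the protocol's planned dose as an overdose, to be reported whether or not it has clinical effects. With two different planned doses for Day 2, the same administration complies with Section 6.4.2 and is arguably an overdose under Section 4.1.1.

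**Working it through.** The protocol states no figure to reproduce. The check sets the sections side by side and works out the daily dose under each.

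**Inputs.** 40 mg bid is 2 × 40 = 80 mg per day. 80 mg bid is 2 × 80 = 160 mg per day. Both regimens are in Sections 4.1 and 6.4.2.

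**Where the sections agree and where they differ** (total daily dose in mg, Days 1, 2, 3, 4):

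| Subject | Section 4.1.1 | Section 6.4.2, literal |
|---|---|---|
| Increase supported on Day 2, 80 mg bid tolerated | 80, 160, 160, 160 | 80, 160, 160, 160 |
| Increase supported on Day 2, 80 mg bid then not tolerated | 80, 160, 80, 80 | 80, 160, 80, 80 |
| Increase not supported on the morning of Day 2, subject still in the study | 80, 80, 80, 80 | 80, 160, 80, 80 |

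Only the third row differs. For Section 6.4.2, that row takes the subject as moved to 40 mg bid on Days 3 and 4.

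- Day 2 difference: 160 − 80 = 80 mg, a factor of 160 / 80 = 2.
- Total over Days 1 to 4: 80 + 80 + 80 + 80 = 320 mg against 80 + 160 + 80 + 80 = 400 mg, again a difference of 80 mg.
- If only the Day 2 morning dose is raised and the evening dose goes back to 40 mg: 80 − 40 = 40 mg.

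**Is the Section 4.1.1 decision available before the first 80 mg dose?** Yes. Table 3 schedules seven bedside glucose values per day: pre-dose and at 2, 4, 6, 9, 12 and 14 hours. Six follow the first Day 1 dose, and the Day 2 pre-dose value comes before that morning's dose. So Section 4.1.1 describes a decision made before 80 mg is given, not a trial of 80 mg followed by a judgement on tolerance.

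**How many subjects?** This cannot be computed. The glucose limits are presumably in Figure 2, which is not shown in the text available, and the protocol gives no expected rate of failing them. The conflict between the sections does not depend on what the limits are.

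**The case against.** The strongest reply is that the intended rule is clear. Section 4.1.1 is the section on titration, it names its inputs, and the synopsis and Sections 4.1 and 4.2 point the same way. Section 6.4.2 itself speaks of maintaining 40 mg bid, which makes best sense for a subject who never left that dose. On this view the sentence is loosely worded rather than a competing rule. Much of this stands, and it is why the point is minor. It does not remove the conflict: the protocol states no order of precedence between its sections, and Section 6.4.2 does not send the reader to Section 4.1.1.

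A second reply is that the affected group is narrow. Section 4.1.2 already discontinues a subject who needs rescue after the initial dose and requires a dose reduction if rescue is needed during titration. Section 2.4 reports that up to 80 mg bid has been given to T2DM patients without raising a safety concern. Both statements are correct and limit the practical risk.

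Two further criticisms are tempting, and the text does not support them:

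- A reader might infer that the 40 mg branch of Section 6.4.2 leaves Day 4 without a dose, by counting its two further days from Day 1. The synopsis and Section 4.1 show that the two days are Days 3 and 4, after the two titration days.
- A reader might infer from the heading of Section 4.1.2 ("Low plasma glucose outside titration period") that the rescue rules do not apply on Days 1 and 2. The scope sentence there covers the residential period apart from 0 to 6 hours post dose on Days 5 and 8, and the last paragraph deals with titration directly. The heading is a clerical matter.

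**Conclusion.** Section 6.4.2 contradicts Section 4.1.1, and also the synopsis and Sections 4.1 and 4.2, on whether the Day 2 increase is conditional. For a subject not eligible for the increase, the literal difference is up to 80 mg on Day 2 (160 mg against 80 mg). It is 40 mg if only the morning dose is raised. This assumes that staff follow Section 6.4.2 alone and that the subject is still in the study on Day 2. The number of such subjects is unknown.

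A reader might infer that the efficacy result is at risk. The documents do not support that. Titration ends before randomisation on Day 5, the dosing rules for Days 3 to 8 agree across sections, and each subject takes the same individual dose in both clamp periods. The glucagon versus control comparison is therefore unaffected. Nor can it be said that a titration rule is missing, since Section 4.1.1 states it and Figure 2 cannot be seen here. What remains is a minor correction to an operative dosing sentence, worth making because it bears on hypoglycaemia risk and on what counts as an overdose.

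**What to change.** In Section 6.4.2, replace the Day 2 sentence with wording such as:

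> On Day 2 the dose is increased to 80 mg bid only if the glucose criteria in Section 4.1.1 and Figure 2 are met; otherwise 40 mg bid is kept, unless the subject is discontinued under Section 4.1.2 or 5.4.3. The Day 2 dose is continued on Days 3 and 4, or reduced to 40 mg bid if needed.

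The cost is one reworded sentence. No visit, sample or analysis changes, because Table 3 already schedules the glucose values on which the decision rests.
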